#### **7.4.2 Treatment Plan Modification for Elevated Serum Creatinine**

If at the time of a planned pamidronate infusion, the patient's serum creatinine level is  $>2$  times that of the baseline level (done at Study Enrollment or Study Entry), pamidronate will be held.

If the creatinine level decreases to  $\leq 2$  times the baseline level within 2 weeks, the pamidronate may be given as planned.

If it remains elevated for more than 2 weeks, the subject will skip the scheduled dose of pamidronate. If at the time of the next pamidronate dose (if applicable) the subject's creatinine level has not returned to  $<2$  times that of the baseline value pamidronate will be permanently discontinued, but the subject will continue vitamin D and calcium supplementation.

#### **7.4.3 Expected Toxicities**

The most common side effects in adults receiving pamidronate are hypertension, injection site reaction, hypocalcemia, hypokalemia, hypomagnesemia, hypophosphatemia, loss of appetite, nausea, vomiting, anemia, urinary tract infectious disease, cough, dyspnea, fatigue, and malaise. Other serious adverse effects that have been observed in adults are arthralgia, aseptic necrosis of bone of jaw, bone pain, myalgia, seizure, deteriorating renal function, focal segmental glomerulosclerosis, and nephrotoxicity.

In studies of pamidronate in children, hypocalcemia is also a common side effect. Brief acute phase reactions, including fever, headache, nausea, vomiting, rash, tachycardia, myalgia, and bone pain have also been noted on first exposure in pediatric patients. Uncommon side effects are nephrotoxicity, anterior uveitis, and atrial fibrillation. Due to these possible side effects, subjects will have laboratory evaluations performed to monitor for hypocalcemia or nephrotoxicity. Furthermore, any safety issue that might arise will be quickly recognized and treated as these subjects will be undergoing intensive monitoring following HCT.

Potential long-term side effects are radiographic metaphyseal bands, iatrogenic osteopetrosis, fractures after discontinuation of drug in growing children, delayed healing at osteotomy sites, esophageal cancer, and osteonecrosis of the jaw.

Long-term side effects are unlikely after a short-term treatment with pamidronate in patients without an underlying metabolic bone disease. There have been no reports of either esophageal cancer or osteonecrosis of the jaw in children after treatment with pamidronate.

Refer to the prescribing information for additional information.

#### **7.4.4 Management of Treatment Related Side Effects**

The research staff will monitor, as well as educate the subject and care providers, on early signs of potentially serious side effects. At each visit beginning at Day 90 post-HCT an assessment for adverse events will be completed per section 9.2.

Included are the following known risks of pamidronate:

1. Allergic reaction most commonly appearing as skin rash with or without itching
2. Anterior uveitis by subject's report (blurred vision, eye pain, redness,

sensitivity to light, irregular pupil)

3. Atrial fibrillation by the subject's report (palpitations, chest pain, shortness of breath)
4. Osteonecrosis of the jaw by subject's report (jaw pain, swelling, redness, or other signs of infection in the gums, gums or sockets that don't heal after dental work, numbness or a heavy feeling in the jaw, draining of pus, visible bone in the mouth, roughness of the gums in a particular area) and/or physical examination at study visits

Medical confirmation of diagnosis and appropriate intervention including, if indicated, referral to a specialist for further care, would be performed.

In the case of CTCAE grade 4 toxicity, no further pamidronate would be given per section 7.3.6.

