#### **7.4.6 Criteria for Discontinuation**

Subjects receiving pamidronate will discontinue pamidronate if any of the following conditions exist:

- Clinically significant allergic reaction (tongue or facial swelling or wheezing) to pamidronate
- Subsequently meets any of the study exclusion criteria (section 5.2) except for clinically significant current fracture, in which case pamidronate will be continued
- If creatinine level increases to > 2 times baseline level and a dose of pamidronate must be skipped for a 2nd time per section 7.3.2.
- Unacceptable toxicity (e.g. osteonecrosis of the jaw)
- Positive pregnancy test - Refer to section 9.3 regarding the reporting of pregnancy during study treatment.
- Disease relapse
- Subject's well-being, in the opinion of the Investigator, would be compromised by continuation of pamidronate administration.

These subjects will continue to be enrolled in the study, receiving vitamin D/calcium and participating in study procedures as planned unless contraindicated. An exception to this plan is for those patients who have a worsening of their disease (relapse) and discontinue routine post-HCT follow-up at the enrolling institution. In this situation, patients would be taken off study with no further study procedures.

Subjects who discontinue pamidronate treatment after the first dose (Day 90) will be included in the statistical analyses as members of the Pamidronate Group under the principle of intention-to-treat.

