## 9.2 Documentation of Adverse Events

The goal of AE monitoring will be to focus on events that are related directly to study participation, not the transplant procedure or the disease under treatment unless study participation exacerbates the event. Due to the complex medical condition of the post-transplant patient, monitoring for adverse events will focus on events beginning with the 1st dose of pamidronate through the Day 360 visit.

For patients assigned to pamidronate, a toxicity assessment will be done in conjunction with each infusion (Day 90, 180, and 270) at the following time points:

- Prior to the pamidronate infusion - within 72 hours before the infusion
- 1 week (+/- 3 days) after each pamidronate infusion via telephone interview
- At any unplanned visit

At each of these time points the worst grade of the targeted toxicity since the previous assessment will be recorded in addition to any unexpected toxicities felt at least possibly related to pamidronate.

Of special concern are rare, but potentially serious risks associated with pamidronate which, if serious enough will lead to the discontinuation of the study drug per section 12.5. These targeted toxicities (based on CTCAE v4) will be collected on all patients (control and pamidronate) are:

- Anterior uveitis by subject's report (blurred vision, eye pain, redness, sensitivity to light, irregular pupil)
- Atrial fibrillation by the subject's report (palpitations, chest pain, shortness of breath)
- Osteonecrosis of the jaw by subject's report (jaw pain, swelling, redness, or other signs of infection in the gums, gums or sockets that don't heal after dental work, numbness or a heavy feeling in the jaw, draining of pus, visible bone in the mouth, roughness of the gums in a particular area) and/or physical examination at study visits.

All targeted toxicities, regardless of grade, and other events, grade 3 or greater that are felt at least possibly related to study treatment or cannot be explained by another cause (i.e. unexpected, not related to transplant, disease for which the transplant was done, underlying medical condition, etc.) will be recorded in OnCore for all patients.

After completion of the targeted toxicity form at day 360 formal collection of adverse events ends; however the sponsor/investigator must report upon knowledge any treatment related event meeting the expedited reporting criteria found in section 9.1 regardless of timing to pamidronate.

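### Allergic reaction is a listed risk in 7.4.4 but not a targeted toxicity in 9.2, so non-serious grade 1-2 allergic and acute-phase reactions to pamidronate would be under-ascertained

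*Combined protocol and SAP*

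**What the plan says.** Section 7.4.4 states: "At each visit beginning at Day 90 post-HCT an assessment for adverse events will be completed per section 9.2". It then lists four known risks as included. The first is "Allergic reaction most commonly appearing as skin rash with or without itching"; the others are anterior uveitis, atrial fibrillation and osteonecrosis of the jaw.

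Section 9.2 introduces its own list with "These targeted toxicities (based on CTCAE v4) will be collected on all patients (control and pamidronate) are" and names only the last three. It then has two recording rules that bear on pamidronate:

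- **At the infusion assessments** (within 72 hours before, by telephone one week after, and at unplanned visits; pamidronate group): "the worst grade of the targeted toxicity since the previous assessment will be recorded in addition to any unexpected toxicities felt at least possibly related" (the drug meant is pamidronate). No grade floor is stated for the unexpected events.
- **In OnCore, for all patients:** "All targeted toxicities, regardless of grade, and other events, grade 3 or greater that are felt at least possibly related to study treatment", or that have no other explanation.

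Section 7.4.3, headed as expected toxicities, says of children: "Brief acute phase reactions, including fever, headache, nausea, vomiting, rash, tachycardia, myalgia, and bone pain have also been noted on first exposure". Section 7.4.6 lists among the reasons to discontinue: "Clinically significant allergic reaction (tongue or facial swelling or wheezing) to pamidronate". Section 9.4 requires the affiliate site to report every serious event whatever its attribution or expectedness.

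**The concern.** The two lists carry nearly the same items, and 9.2 gives no reason for leaving allergic reaction out. A site following 7.4.4 would expect 9.2 to capture it. A site following 9.2 would have no instruction to enter a mild one.

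The same gap covers the acute-phase reaction. The background (Section 1.2) names it, with transient hypocalcemia, as one of the more likely side effects in children, and 7.4.3 ties it to first exposure. The protocol already pays for an adverse-event call after each infusion, but 9.2 does not require that call to record a non-serious fever, myalgia, bone pain or rash below grade 3.

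At stake is the completeness of the harms data for a drug that the protocol says is not approved in children. Section 9.2 gives as its goal the events that come directly from taking part in the study rather than from the transplant, and a reaction to an infusion fits that goal. The primary endpoint is not affected.

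**Working it through.** The documents state no figure to reproduce. The check takes each kind of event through the rules.

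**Step 1: is the event unexpected?** Section 9.1 calls an event unexpected if it is not listed, or not listed at the specificity or severity seen, in the brochure or other risk information. Allergic reaction is listed in 7.4.4, and acute-phase reaction with its symptoms in 7.4.3. At the severity described there, neither is unexpected, so the route "in addition to any unexpected toxicities felt at least possibly related to pamidronate" does not apply.

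**Step 2: is it targeted?** No. Only uveitis, atrial fibrillation and osteonecrosis of the jaw are.

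**Step 3: does it meet the general rule?** Only at grade 3 or higher.

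| Event after pamidronate, possibly related | Recording rule |
|---|---|
| Allergic reaction, grade 3+ | Recorded (9.2) |
| Allergic reaction, grade 1-2, non-serious | None in 9.2, despite 7.4.4 |
| Acute-phase reaction, grade 3+ | Recorded (9.2) |
| Acute-phase reaction, grade 1-2, non-serious | None in 9.2 |
| Either, if serious, at the affiliate site | Reported (9.4) |

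Two related points came up:

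- Rash is both the usual sign of allergic reaction (7.4.4) and an acute-phase symptom (7.4.3), so a low-grade rash has no clear category.
- Section 9.2 records the targeted three at every grade, while 12.5 says they are recorded only from grade 3 up. Both cannot hold.

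**Step 4: illustrative size.** Section 12.1 plans 86 subjects at Day 90. With equal allocation, 86 / 2 = 43 would receive pamidronate, and three infusions each gives at most 43 × 3 = 129 infusions. The reaction rate is an assumption:

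- 10%: 43 × 0.10 = 4.3 children
- 30%: 43 × 0.30 = 12.9 children
- 50%: 43 × 0.50 = 21.5 children

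If every reaction stayed at grade 1-2 and non-serious, none would have to be entered under 9.2. With 0 of 43 recorded, the one-sided 95% upper bound is 1 − 0.05^(1/43) = 6.7%. That bound is valid for grade 3+ reactions. It says nothing about reactions of any grade.

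**The case against.** The strongest defence is that selective recording is a deliberate choice. Section 9.2 explains that the medical condition of these patients is complex, so monitoring concentrates on chosen events, and the revision history shows that 9.2 was clarified in versions 9 and 9A. Section 11 has no tolerability endpoint. This stands as a reason not to collect all low-grade events in everyone. It does not explain why 7.4.4 includes a risk that 9.2 then leaves off its list.

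A reader might infer from the two lists that 9.2 collects nothing but the three targeted toxicities, or that mild reactions can never reach the data. The documents do not support that. Section 9.2 also takes in possibly related or unexplained events of grade 3 or higher, and possibly related unexpected events with no grade floor; 9.4 adds serious events at the affiliate site.

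A reader might also infer that early allergic signs would be missed clinically. That does not follow either. Section 7.4.4 requires staff to watch for early signs and have them medically confirmed, history is reviewed at each visit (8.2.1), unscheduled visits are allowed (8.2.6), and discontinuation under 7.4.6 does not depend on an OnCore entry.

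Three further limits stand:

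- The targeted toxicity form was moved to a case report form that is not in the documents, so a field for allergic reaction may exist. It would not remove the conflict in the text.
- Acetaminophen is given before each infusion, and Section 1.2 says such agents can mitigate the reaction, so the assumed rate could be too high.
- The protocol does not say that the one-week call was timed to catch these reactions.

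**Conclusion.** The point holds as under-ascertainment. Section 7.4.4 includes allergic reaction in an assessment that 9.2 does not target, and under 9.2 as written non-serious grade 1-2 allergic and acute-phase reactions have no recording rule. Their any-grade incidence could not be reported.

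It would go too far to say that these harms would be reported wrongly. Grade 3+ events are captured, and a result of 0 of 43 would mislead only if someone presented it as covering all grades, which the documents do not plan.

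The figures of 4 to 22 children and 6.7% are illustrations. They rest on an assumed rate of 10-50%, and 43 is an upper limit because the planned 86 makes no stated allowance for subjects who fail the Day 90 randomization checks in 6.2. The conclusion itself rests only on the text. The change is worth making but is not critical: neither the primary analysis nor the 12.5 monitoring comparison depends on it.

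**What to change.** - Reconcile 9.2 with 7.4.4: in the pamidronate group, record allergic reaction, and preferably acute-phase reaction, at any grade at the existing pre-infusion, one-week call and unplanned-visit assessments.
- Enter them as a separate item. Section 9.2 reserves the targeted category for uncommon but possibly serious risks and ties it to 12.5, which brief expected reactions do not fit. The three-toxicity comparison in 12.5 then stays as it is.
- State how a low-grade rash is to be classified, since it appears under both headings.
- Tabulate the new item by infusion number, and label any other adverse-event summary as grade 3 or higher.
- Make 9.2 and 12.5 agree on whether the targeted three are recorded at every grade or only from grade 3.

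No new visit or call is needed, and no change to dosing or stopping rules is proposed. The cost is some extra low-grade data entry, and mild symptoms after transplant are hard to attribute. If the sponsor prefers not to collect them, 7.4.4 should be brought into line with 9.2 and reports should say that low-grade expected reactions were not collected.

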#### **7.4.5 Pregnancy Testing and Contraception Use**

Since pamidronate is in the category D pregnancy risk group, a pregnancy test will be done within 72 hours prior to each dose and no further pamidronate will be given in the event of a positive result. Refer to section 9.3 regarding the reporting of pregnancy during study treatment. Post-menarchal subjects randomized to pamidronate will be put on an oral contraceptive pill (Loestrin or Orthocept or other OCP that contains 30 mcg ethinyl estradiol) or a birth control patch (e.g. Ortho Evra) or other effective means of birth control.

#### **7.4.6 Criteria for Discontinuation**

Subjects receiving pamidronate will discontinue pamidronate if any of the following conditions exist:

- Clinically significant allergic reaction (tongue or facial swelling or wheezing) to pamidronate
- Subsequently meets any of the study exclusion criteria (section 5.2) except for clinically significant current fracture, in which case pamidronate will be continued
- If creatinine level increases to > 2 times baseline level and a dose of pamidronate must be skipped for a 2nd time per section 7.3.2.
- Unacceptable toxicity (e.g. osteonecrosis of the jaw)
- Positive pregnancy test - Refer to section 9.3 regarding the reporting of pregnancy during study treatment.
- Disease relapse
- Subject's well-being, in the opinion of the Investigator, would be compromised by continuation of pamidronate administration.

These subjects will continue to be enrolled in the study, receiving vitamin D/calcium and participating in study procedures as planned unless contraindicated. An exception to this plan is for those patients who have a worsening of their disease (relapse) and discontinue routine post-HCT follow-up at the enrolling institution. In this situation, patients would be taken off study with no further study procedures.

Subjects who discontinue pamidronate treatment after the first dose (Day 90) will be included in the statistical analyses as members of the Pamidronate Group under the principle of intention-to-treat.

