## **5.2 Exclusion Criteria**

Patients will be excluded from participation in the study if any of the following conditions exist:

- 5.2.1** History of a primary bone malignancy involving the lumbar spine
- 5.2.2** Treatment with other biphosphonates, Denosumab, or Teriparatide within one year prior to enrollment
- 5.2.3** Pregnancy or breastfeeding – menstruating females must have a negative pregnancy test prior to study enrollment and agree to repeat pregnancy testing and contraception use per protocol as pamidronate is Pregnancy Category D – positive evidence of human fetal risk based on adverse reaction data
- 5.2.4** Renal insufficiency, defined as creatinine level greater than the upper limit of normal for age
- 5.2.5** Hereditary metabolic bone disease or skeletal dysplasia (e.g., osteopetrosis or OI) or primary hyperparathyroidism
- 5.2.6** Non-malignant diseases with underlying metabolic defects that may affect bones such as Hurler's syndrome and other Mucopolysaccharidoses and osteopetrosis, or diseases where the use of hematopoietic cell transplant itself is still under investigation, primarily, epidermolysis bullosa.
- 5.2.7** Patients with diseases that have increased sensitivity to chemotherapy or radiation including (but not limited to) Fanconi anemia, dyskeratosis congenita.
- 5.2.8** Clinically significant fractures as defined by ISCD (a long bone fracture of the lower extremities, vertebral compression fracture, or two or more long bone fractures of the upper extremities) (88,89) indicated by a cast or a spine x-ray within the last 2 weeks
- 5.2.9** Known or suspected allergy to pamidronate or related products
- 5.2.10** Planned administration of an investigational study drug or agent that either can interact with pamidronate or have an independent effect on bone mineral density within the 4 weeks prior to randomization (Day 90) or planned use during study participation (Day 90 through Day 360)
- 5.2.11** Impending invasive dental procedure that would be expected to occur during study participation (through Day 360)

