### **6.2 Randomization (Day 90 Post-HCT Visit +/- 14 days)**

Randomization to pamidronate (Pamidronate Group) or no pamidronate (Control Group) will occur at Day 90 (+/- 14 days) by the institutional study coordinator based on the randomization schedule developed by the study statistician and entered into OnCore.

A brief review of continuing eligibility will be done and subjects will not be eligible for randomization if one or more of the following are true:

- Vitamin D ( $D_2+D_3$ )  $<20$  ng/ml as use of pamidronate is contraindicated due to potentially higher risk of hypocalcemia. Levels should be measured within 14 days prior to randomization.\*\*†
- serum creatinine is  $> 2$  times the baseline value (at Study Entry) - perform within 14 days prior to randomization
- an investigational study drug or agent, including biphosphonates, Denosumab, or Teriparatide, was administered within the previous 4 weeks or is planned for use during study participation (Day 90 through Day 360)
- positive pregnancy test (performed within 14 days prior to randomization)
- Inability to successfully complete a DEXA scan
- the parent or adult patient refuse randomization
- disease relapse has occurred

The randomization will be stratified by age with 2 strata:  $< 10$  years old and  $\geq 10$  years old.

If the patient is ineligible for or refuses randomization, no further research related procedures or treatment will occur after the Day 90 visit; however permission to continue review of the patient's medical record through the Day 360 visit for routine clinical information is embedded within the consent form document. This information will be collected only if the patient continues care at the enrolling

institution. Patient care will be at the discretion of the treating physician(s) and independent of this study.

OnCore will automatically generate an email alerting key study personnel of the randomization (or lack of).

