### 7.3.2 For Low vitamin D ( $D_2+D_3$ ) Levels

Age	$<9$	Vitamin D	Calcium (elemental)
Vitamin D level ( $D_2+D_3$ ) f	20-29	• 4000 IU/day of vitamin D supplementation x 4 weeks	• No supplementation
ionized or corrected calcium level	normal		
dietary calcium intake based on questionnaire	sufficient	• Vitamin D ( $D_2+D_3$ ) level should be checked in 4 or 8 weeks and continue supplementation if needed • Once the Vitamin D level is normalized the participant would receive 600 IU/day of Vitamin D	

Age	$\geq 9$	Vitamin D	Calcium (elemental)
Vitamin D level ( $D_2+D_3$ ) T	20-29	
 
• 4000 IU/day of vitamin D supplementation x 8 weeks
 
	
 
• No supplementation
 

ionized or corrected calcium level	normal	
 
• Vitamin D (<math>D_2+D_3</math>) level should be checked in 4 or 8 weeks and continue supplementation if needed
 
	
dietary calcium intake based on questionnaire	sufficient	
 
• Once the Vitamin D level is normalized the participant would receive 600 IU/day of Vitamin D
 
	

Age	1-3 Years	Vitamin D	Calcium (elemental)
Vitamin D level ( $D_2+D_3$ ) T	20-29	
 
• 4000 IU /day of vitamin D supplementation x 4 weeks
 
	
 
• calcium 600 mg/day
 

ionized or corrected calcium level	normal	
 
• Vitamin D (<math>D_2+D_3</math>) level should be checked in 4 or 8 weeks and continue supplementation if still low
 
	
dietary calcium intake based on questionnaire	low	
 
• Once the Vitamin D level is normalized the participant would receive 600 IU/day of Vitamin D
 
	

Age	4-8 years	Vitamin D	Calcium (elemental)
Vitamin D level (D 2 +D 3 ) T	20-29	
 
• 4000 IU/day of vitamin D supplementation x 4 weeks
 
• Vitamin D (D2+D3) level should be checked in 4 or 8 weeks and continue supplementation if still low
 
• Once the Vitamin D level is normalized the participant would receive 600 IU/day of Vitamin D
 
	
 
• calcium 1,000 mg/day
 

ionized or corrected calcium level	normal		
dietary calcium intake based on questionnaire	low		

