**7.4 Pamidronate**

**7.4.1 Treatment Plan**

Subjects randomized to the Pamidronate Group will receive 3 single doses of pamidronate at 3-month intervals (Day 90 +/-14 days, Day 180 +/-14 days, and Day 270 +/-30 days).

Note: All time point specific laboratory testing procedures (sections 8.1 and 8.3) must be collected prior to the pamidronate infusion (except those specifically designated post infusion); however for ease of scheduling the consultations as well as the Day 90 DXA and Day 90 pQCT may be performed after the infusion as long as done within the +/-14 day window. Ionized calcium or corrected calcium, and Vitamin D levels (D2+D3) will be drawn prior to pamidronate infusions. If either are low, the subject should receive supplemental calcium and/or Vitamin D per Section 7.3. If the subject is receiving supplemental calcium, an ionized or corrected calcium level should be drawn after the pamidronate infusion end but prior to discharge from clinic on the day of the pamidronate.

Prior to each infusion the patient will be assessed and pamidronate will be held if:

- Serum creatinine is > 2 times the baseline (Study Entry) level – refer to section 7.3.2 for monitoring plan – the pre-treatment creatinine may be done anytime within 72 hours prior to the planned pamidronate administration

- Pregnancy test is positive (subject will permanently discontinue study drug) per section 7.3.5 – pregnancy testing may be done anytime within 72 hours prior to the planned pamidronate administration

Pamidronate 1 mg/kg (to a max dose of 60 mg) will be administered via a single IV infusion over 4 hours using a line separate from all other drugs. Dosing will be based on the patient's actual weight or, if overweight, on ideal body weight (IBW). This will be followed by a normal saline flush of 20 cc total given at the same rate as the pamidronate.

Premedication: Subjects will be given 15 mg/kg acetaminophen (or maximum of 500 mg) prior to pamidronate infusion then every 4 hours as needed for a maximum of 24 hours.

Post-Pamidronate Infusion Laboratory Tests: A serum calcium level will be done after the pamidronate infusion end but prior to discharge from clinic on the day of the pamidronate.

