#### Laboratory Reference Ranges

	University of Minnesota (UMN)		Fred Hutchinson Cancer		
Creatinine (mg/dL)	0-21d	0.33-1.01	2 months-2 years	0.1-0.4	
	22 days-8 years	0.15-0.53			
	9-14 years	0.39-0.73		0.1-0.6	
	15-19y	0.5-1.0		0.2-0.9	
	20 y and older, F	0.52-1.04		0.2-1.1	
Calcium ("corrected calcium"?)	20 y and older, M	0.66-1.25	≥14 years	8.7-10.7	
	Age	mg/dL			
	0-11 mo	8.5-10.7			
	1-18 yr	9.1-10.3			
	19 yr & older	8.5-10.1			
Ionized Calcium	Age	mg/dL			
	0-11 mo	5.1-6.3			
	1 yr and older	4.4-5.2			
Vit D (D2 + D3) / 25-hydroxy (OH) vitamin D (ng/mL)	20-75		30-100		
Intact parathyroid hormone (iPTH) (pg/mL)	12-72pg/mL		12-75		
Interleukin (IL)-6 (pg/mL)	≤3.0		≤3.0		
IL-7 (pg/mL)	0.66-9.2		0.66-9.2		
Tumor necrosis factor alpha (TNF- $\alpha$ ) (pg/mL)	≤8.8		≤8.8		

a IL-6, IL-7, and TNF- $\alpha$  samples from Fred Hutchinson Cancer Research Center will be analyzed at UMN.

Laboratory normal ranges for CTX, DPD, P1NP, OCN, RANKL, and OPG vary with age. Urinary DPD will be adjusted for urinary creatinine content.

If total calcium or vitamin D (D2+D3)/25-OH vitamin D is below the normal range, supplementation will be administered per Section 7.3.

If creatinine level for a subject randomized to receive pamidronate becomes elevated during the study (creatinine level  $>2$  times the baseline value at Study Entry) refer to section 7.3.2 for treatment modification and monitoring.

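### Section 7.4.6 stops pamidronate once creatinine exceeds the upper limit of normal for age, while five other places act only above 2 times baseline, and no sentence says which limit governs

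*Combined protocol and SAP*

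**What the plan says.** The protocol uses two creatinine limits for the same drug.

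**ULN for age.** Exclusion 5.2.4 reads "Renal insufficiency, defined as creatinine level greater than the upper limit of normal for age". Section 7.4.6 stops pamidronate if any one of its listed conditions exists, and its second item is "Subsequently meets any of the study exclusion criteria (section 5.2) except for clinically significant current fracture". Current fracture is the only exclusion exempted. No route back to dosing is given.

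**2 times baseline.** Five places use this limit:

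- 6.2 bars randomisation at Day 90 if creatinine is more than twice the Study Entry value.
- 7.4.1 holds an infusion if "Serum creatinine is > 2 times the baseline (Study Entry) level".
- 7.4.2 holds above 2 times baseline and lets the dose be given if creatinine falls back to that limit or below within 2 weeks. Otherwise: "If it remains elevated for more than 2 weeks, the subject will skip the scheduled dose of pamidronate". Pamidronate ends for good only if the value is still raised at the next dose.
- 8.3.5, under the reference ranges, treats creatinine as elevated when it is more than 2 times baseline.
- The third item of 7.4.6 reads "If creatinine level increases to > 2 times baseline level and a dose of pamidronate must be skipped", and applies at the second skip.

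Children who stop after the first dose stay in the Pamidronate Group under intention-to-treat (7.4.6, 12.2).

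**The concern.** A child whose creatinine is above ULN but not above 2 times baseline meets a stop condition in 7.4.6, yet 7.4.1 and 7.4.2 give no reason to withhold the infusion. Staff at two sites could each follow the written protocol and handle the same value differently.

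The choice matters in both directions. Under the stricter reading, a child may receive one of three planned infusions and still be analysed as treated. Under the looser one, a child who fits the protocol's own definition of renal insufficiency keeps receiving a drug for which 7.4.3 lists nephrotoxicity as an uncommon paediatric effect. Pamidronate is the only randomised component, so the stopping rule decides how much of the intervention is delivered.

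**Working it through.** The plan states no figure on this point, so there is none to reproduce. The check compares the two limits.

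**Inputs.** The creatinine reference ranges (mg/dL) in 8.3.5, the ULN limit in 5.2.4 and the 2-times limit in 7.4.1 and 7.4.2. Baseline and test are assumed to fall in the same age band.

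**Where the rules diverge.** The stop applies and the hold does not when

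ULN < value ≤ 2 × baseline.

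Such values exist only if 2 × baseline > ULN, that is, baseline > ULN/2.

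**UMN**

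| Age band | Range | ULN/2 | 2 × lower limit | Baselines at which the rules diverge |
|---|---|---|---|---|
| 22 days-8 years | 0.15-0.53 | 0.265 | 0.30 | above 0.265 |
| 9-14 years | 0.39-0.73 | 0.365 | 0.78 | every in-range value |
| 15-19 years | 0.5-1.0 | 0.50 | 1.00 | every in-range value above 0.50 |
| 20 and older, F | 0.52-1.04 | 0.52 | 1.04 | every in-range value above 0.52 |
| 20 and older, M | 0.66-1.25 | 0.625 | 1.32 | every in-range value |

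Example, age 9-14: a mid-range baseline is (0.39 + 0.73)/2 = 0.56, so 7.4.1 holds only above 2 × 0.56 = 1.12. A pre-infusion value of 0.80 is above 0.73 and below 1.12. It meets the 7.4.6 stop and does not meet the 7.4.1 hold.

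**Does the literal stop leave 7.4.2 any work?** At UMN from age 9 up, twice the lower limit is at or above ULN in every band (0.78 against 0.73; 1.00 against 1.00; 1.04 against 1.04; 1.32 against 1.25). Any value above 2 times an in-range baseline is therefore already above ULN. If the second item of 7.4.6 is applied as written, the hold, skip and resume scheme and the second-skip test in the third item never operate for these patients.

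Under age 9 at UMN the order reverses for baselines below 0.265. A baseline of 0.20 gives a hold above 0.40, which is reached before 0.53.

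**Fred Hutchinson.** The printed ranges are 0.1-0.4, 0.1-0.6, 0.2-0.9 and 0.2-1.1. The age labels are not fully legible in the text available, but this comparison within each row does not need them. ULN/2 is 0.20, 0.30, 0.45 and 0.55, and the rules diverge for baselines above those values. Twice the lower limit is 0.2, 0.2, 0.4 and 0.4, below ULN in every row, so 7.4.2 keeps some work for low baselines there.

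**Size of rise needed.** From a mid-range UMN baseline, ULN is reached at 0.53/0.34 = 1.56, 0.73/0.56 = 1.30 and 1.0/0.75 = 1.33 times baseline in the three bands under age 20. That is a rise of 30-56%, whereas 7.4.2 acts only above 100%.

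**The case against.** The strongest answer is that the provisions can be applied together: hold above 2 times baseline, and stop if any 7.4.6 condition exists. No section commands a dose at up to 2 times baseline. Section 7.4.1 says when to hold, 6.2 says when not to randomise, and 7.4.2 only says the dose may be given. This part stands. A reader might infer that one section orders discontinuation while another orders the infusion, and the text does not go that far. But the combined reading does not remove the problem: at UMN from age 9 up it empties the 7.4.2 scheme and the third item of 7.4.6 for every in-range baseline. A procedure written out in that detail was presumably meant to operate.

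Intent can be argued either way. Five places use 2 times baseline, which suggests that limit was meant. The drafters also wrote an exemption into the second item for fracture and none for creatinine, which suggests the opposite. Neither argument replaces a sentence in the protocol.

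A reader might also infer that a child randomised at Day 90 above ULN has already met the stop. Section 7.4.6 concerns subjects receiving pamidronate who later meet an exclusion, so its application before the first dose is arguable. The conflict does not depend on it.

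Finally, there are partial safeguards: teleconferences with the affiliate site, initially at least monthly (10.1), at least quarterly review by the monitoring council (10.4), and the investigator's well-being stop in 7.4.6. They may catch individual cases. They do not say which limit applies.

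**Conclusion.** The point holds as an internal contradiction in the stopping rule and should be corrected. The divergence covers every in-range UMN baseline at age 9-14, nearly all in-range UMN baselines from 15 up (all except one exactly at the lower limit in two bands), UMN baselines above 0.265 mg/dL under age 9, and the upper part of each Fred Hutchinson range. This rests on the printed ranges and on baseline and test sharing an age band; the statements about every in-range baseline also assume baselines not below the lower limit.

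The documents do not give the frequency of such values, so the effect on the result is unknown. A reader might infer that the sites have acted differently or that the trial loses power; neither is shown. All randomised children remain in the analysis as assigned, and nominal power does not change. For illustration only, assume a full-course effect of 0.75 SD (the detectable difference in 12.1) and 30 children analysed in the Pamidronate Group. Each child stopped after the first dose would then lower the mean effect by between 0 (one dose suffices) and 0.75/30 = 0.025 SD (one dose does nothing).

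**What to change.** Have the medical lead confirm one limit, because keeping or relaxing a ULN stop is a safety decision.

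- **If the limit is 2 times baseline**, extend the exception in the second item of 7.4.6 with: *and creatinine above ULN (5.2.4), which is handled only by 7.4.2*. The downside is that children above ULN but not above 2 times baseline keep being dosed. Sections 6.2 and 7.4.1 already accept this, and the investigator's well-being stop remains.
- **If the limit is ULN**, write it into 6.2, 7.4.1, 7.4.2 and the third item of 7.4.6 together. The cost is more missed infusions, in a number the documents do not allow one to estimate.

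For children already treated, count by site the pre-infusion creatinine values above ULN for age but not above 2 times baseline, and report how many were followed by an infusion. Creatinine results are recorded in OnCore (8.3.2), so the count needs no new samples or visits.

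As a separate clerical correction, update the outdated section numbers. For example, 8.3.5 says "refer to section 7.3.2 for treatment modification and monitoring", but that number now heads the low vitamin D chart and the creatinine procedure is 7.4.2. Several other cross-references in Sections 7 and 8 have the same fault and should be checked throughout.
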